3.3 Subject Selection

Written informed consent for study participation will be obtained before any study-related procedures or assessments are performed. All potential subjects will be screened for potential participation, and those meeting all eligibility criteria will be offered participation in the study.

A large black rectangular redaction box covers the majority of the page content, from approximately y=111 to y=250. The box is positioned horizontally across the page, with a small white rectangular gap on the right side and a small black square at the top left corner.

3.5 Treatment Assignment & Blinding

An interactive web response system (IWRS) will be used to ensure study drug inventory, accountability, and appropriate cohort allocation and blinded treatment assignment. The site's unblinded pharmacist or designee will have access to the IWRS and all treatment assignments.

After informed consent has been obtained, all screening procedures have been assessed, and study eligibility has been confirmed, subjects will be randomized to receive either EQ001 or placebo on Study Day 1. The unblinded study pharmacist or designee will access the IWRS to randomize the subject into the study, receive the unblinded treatment assignment and dose, record drug accountability, and request resupply. EQ001 will be administered Q2W for 8 weeks (a total of 5 doses) at the following dose levels:

- **Cohort 1:** Randomized 3:1 (EQ001: Placebo)
 - EQ001 0.8 mg/kg
 - Placebo
- **Cohort 2:** Randomized 3:1 (EQ001: Placebo)
 - EQ001 1.6 mg/kg
 - Placebo
- **Cohort 3:** Randomized 3:1 (EQ001: Placebo)
 - EQ001 2.4 mg/kg
 - Placebo
- **Cohort 4:** Randomized 3:1 (EQ001: Placebo)
 - EQ001 3.2 mg/kg
 - Placebo

[figure not shown]
EQ001 or placebo doses will be administered in the clinic; subjects will be observed for a minimum of 30 minutes after administration.

Investigators, site staff, and subjects will be blinded to treatment assignment. The Sponsor may be unblinded to treatment assignment. The unblinded pharmacist or designee will be instructed not to divulge the treatment administered to any subject with the blinded site personnel, study subject or blinded study monitor and any other blinded CRO/vendor team members.

[figure not shown]
The blind should be broken only if knowledge of the subject's treatment allocation would facilitate specific emergency treatment. Unblinding procedures are provided in the Pharmacy and IWRS Manuals. The investigator should contact the Sponsor and/or designee prior to unblinding a subject's treatment assignment. In the event of an emergency when unblinding is necessary and the Sponsor and/or designee could not be contacted, the investigator must contact the Sponsor and/or designee as soon as possible after the unblinding. Treatment assignment may be provided to the study sites/subjects after database lock.

Following final database lock all roles may be considered unblinded.

This document is confidential.

This document is confidential.

4 Endpoints

4.1 Primary Endpoint

The primary endpoint of the study is safety and tolerability of EQ001, as assessed by treatment-emergent adverse events (TEAEs), treatment emergent serious adverse events (TESAEs), clinical laboratory values, electrocardiograms (ECGs), vital signs and physical examinations.

4.2 Secondary Endpoints

The secondary endpoints of the study are:

- Pharmacokinetics of EQ001, as assessed [REDACTED]
[REDACTED]
[REDACTED]
[REDACTED]
- Clinical activity of EQ001, as assessed by the following variables:
 - Change from baseline in prebronchodilator FEV1
 - Change from baseline in fractional exhaled nitric oxide (FeNO)
 - Change in peak expiratory flow rate (PEFR)
 - Change from baseline in Asthma Control Questionnaire (ACQ-6) score
 - Time to first exacerbation (any severity)
 - Asthma symptoms, peak expiratory flow rate measurements, use of controller and rescue medication, nighttime awakening due to asthma and asthma-related activity limitations (as recorded on an eDiary)
 - Annualized rate of asthma exacerbations (of any severity)

5 Analysis Populations

5.1 Safety Population

The Safety Population consists of all subjects who receive any study drug. Subjects will be analyzed according to treatment actually received.

5.2 Efficacy Population

The Efficacy Population consists of those subjects in the Safety Population who have at least 1 post-treatment clinical activity assessment.

5.3 Pharmacokinetic (PK) Analysis Population

The pharmacokinetic population consists of those subjects in the safety population who have at least 1 measurable post-EQ001 exposure EQ001 serum concentration.

[REDACTED]

[REDACTED]

6 General Aspects for Statistical Analysis

[figure not shown]
[figure not shown]
6.1 General Methods

Statistical analysis of data from this study will be performed using SAS version 9.4 or more recent version.

Summaries of baseline demographics will be presented for pooled Placebo group from all Cohorts, EQ001 treatment group from each Cohort, pooled EQ001 treatment groups from all Cohorts and Total for all Cohorts. Efficacy will be presented for the pooled Placebo group, EQ001 treatment groups from each Cohort and pooled EQ001 treatment groups. In addition, Safety tables will also include a Total, all subjects pooled, column.

- As the objective of this Phase 1b study is to characterize the safety and tolerability of EQ001, formal statistical hypothesis testing will not be performed. Although exploratory confidence intervals (CIs) may be presented, these data will be used for exploratory conclusions only.
- Statistical analyses will be descriptive in nature. Continuous variables will be summarized using the number of observations (n), mean, standard deviation (SD), median, minimum, and maximum. Categorical variables will be summarized using number of observations (n), frequency and percentages of subjects.
- All relevant subject data will be included in listings. All subjects entered into the database will be included in subject data listings. If applicable, the relative day (i.e., relative to date of first dose of study treatment) of all complete dates will be presented in subject listings.
- For analysis using nominal visits, data collected at unscheduled visits will be included in the subject listings but will not be included in by-visit summary tables, unless otherwise specified.
- Adverse events will be coded for summarization using the Medical Dictionary for Regulatory Activities (MedDRA® Version 22.0). Concomitant medications will be coded using the World Health Organization (WHO) Drug Dictionary Global B3 (March 2019 Version).

This document is confidential.

6.2 Key Definitions

- **Relative study day:** A relative study day is a day of any study assessment relative to the first dose of study drug. The day of the first dose of the study drug will be considered as Day 1 (Visit Day 1 per protocol). Pre-treatment and on-treatment study days are numbered relative to the day of the first dose of study drug. The preceding day of the first dose of the study drug will be considered as Day -1 and next day after the first dose of the study drug will be considered as Day 2 and so on. There will not be a study day of Day 0.
- **Baseline Value:** Unless indicated otherwise, baseline value of a variable is defined as the last non-missing value on or prior to the first dose of study drug. If there are two values qualifying for the baseline value (e.g., FeNO measurements are taken in duplicate), the average of the two will be considered as the baseline value.

This document is confidential.

6.4 Pooling of Centers

Data from all the sites will be pooled together for the analyses, and there is no plan to summarize the data by center/site due to the small number of subjects enrolled at each site.

This document is confidential.

7 Non-Efficacy Data Summaries

7.1 Subject Disposition

Subject disposition data will be summarized using the Safety Population and will include the number and percent of subjects randomized, treated, and replaced. The number and percent of subjects completing treatment and study, and the number and percent of subjects discontinuing treatment and discontinuing the study, by primary reason for discontinuation. Subject enrollment will be summarized by study site. The continuous summary statistics will be presented for the follow-up duration, where the follow-up duration in weeks will be calculated as:

Follow-up duration (weeks) = (date of last contact – date of first dose of study drug + 1) / 7, rounded to 1 decimal place. The number and percent of subjects who failed screening, along with the reasons for screen failure, will be presented for all subjects who signed informed consent. By-subject listings will also be created for disposition data.

7.3 Demographic and Baseline Characteristics

A summary of demographics and baseline characteristics will be presented using the Safety Population. The following variables will be summarized using continuous or categorical descriptive statistics as appropriate:

- Age (years)
- Sex
- Race
- Ethnicity
- Height (cm)
- Baseline Weight (kg)
- BMI (kg/m²)
- Prior Asthma Exacerbations, n (%)
- Baseline FeNO measurement (ppb)
- Baseline Total Serum IgE (IU/mL)
- Baseline ALC (10⁹/L)
- Baseline Total Eosinophil Count (10⁹/L)
- Baseline ACQ-6

This document is confidential.

- Baseline Pulmonary Function Test (PFT) results including pre-bronchodilator FEV1 (L/min) absolute, forced vital capacity (FVC) (L), FEV1/FVC (%), and FEV1

A by-subject listing will also be created for demographics and baseline characteristics data.

7.4 Baseline Disease Characteristics

Baseline disease characteristics include time from initial diagnosis of asthma to first dose date and will be presented using continuous summary statistics using the Safety Population. Time from diagnosis of asthma in years will be calculated as (year of first dose – year of diagnosis) + 1. Year of the date of diagnosis will always be present. A by-subject listing will also be created.

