This is a phase 1b, randomized, double-blind, placebo-controlled study to evaluate the safety, tolerability, PK, [REDACTED] clinical activity of EQ001, a humanized immunoglobulin G1 (IgG1) monoclonal antibody that selectively targets CD6 on T_{eff} cells, in subjects with moderate-to-severe uncontrolled asthma. The study will initially enroll up to 32 subjects in up to 4 successive dose cohorts of 8 adult subjects each (up to 10 subjects may be enrolled to achieve 8 DLT evaluable subjects). Doses of 0.8, 1.6, 2.4, and 3.2 mg/kg EQ001, or an equivalent volume of placebo, will be administered subcutaneously (SC) every 2 weeks (Q2W) for a total of 5 doses. Subjects will be randomized in a 3:1 ratio (active:placebo) to characterize the safety, tolerability, PK, PD, and clinical activity of ascending SC doses of EQ001 and to determine the maximum tolerated dose (MTD). After determination of the MTD, and at the Sponsor's discretion, the MTD cohort may be repeated to increase the number of subjects receiving the MTD to 12 and subjects in the pooled placebo cohort to 10; therefore, the total number of subjects enrolled in the study may be up to 40.

Written informed consent for study participation will be obtained before any study-related procedures or assessments are performed. All potential subjects will be screened for potential participation, and those meeting all eligibility criteria will be offered participation in the study.

The study will be conducted in the following 3 defined periods:

1. **Screening Period:** Will begin when the informed consent form (ICF) is signed. During this period, the subject will undergo baseline assessments to determine eligibility for study participation. The subject will complete an electronic diary (eDiary) to record asthma symptoms, AM and PM peak expiratory flow rate measurements, use of controller and rescue medication, nighttime awakening due to asthma and asthma-related activity limitations. The Screening Period duration will be up to 4 weeks; it will end after at least 2 weeks of baseline assessments have been conducted and all studies required to meet eligibility have been completed. If a subject meets all eligibility criteria (including documented compliance with eDiary completion, peak flow monitoring and adherence to their standard-of-care [SoC] meds), they will be enrolled into the study.

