10.2.2 Medical and Surgical Histories

The investigator or designee will collect the subject's medical and surgical histories, including information on the subject's concurrent medical conditions. All findings will be recorded on the medical history eCRF.

A *complete medical history* at the Screening Visit will include, but will not be limited to, the following information:

- Date of diagnosis of asthma
- Current medications
- Past medications
- History of hospitalization and intubations for asthma
- History of allergies
- History of asthma exacerbations

The subject's interval history of asthma exacerbations is to be obtained at every scheduled study visit (except Day 4); *clinically significant asthma exacerbation* is defined as a > 20% decrease in AM or PM peak flow measurements sustained for 2 days, a doubling of the inhaled corticosteroid dose, initiation of an oral corticosteroid burst for asthma or an emergency department visit/hospitalization for asthma.

A *complete surgical history* at the Screening Visit will include, but not be limited to, any history of upper or lower airway surgeries, such as sinus or laryngeal surgery. An *interval surgical history* is to be obtained at every scheduled study visit (except Day 4 and any unscheduled visits).

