13.5 Demographics and Baseline Characteristics

Demographics and other baseline characteristics will be summarized for the subjects in the safety population. Demographic data will include age, gender, race, and ethnicity. Baseline characteristics data will include (but not be limited to) total serum IgE, FeNO, ACQ-6, and PFT (FEV1 absolute, FVC, FEV1/FVC ratio, and FEV1 %) with bronchodilator reversibility. Medical history data will include (but not be limited to) time from diagnosis of asthma to Screening, prior and current medications used for asthma control, history of biologic therapy use for asthma control, hospitalizations, and intubations.

[REDACTED]

[REDACTED]

[REDACTED]

[REDACTED]

[REDACTED]

[REDACTED]

[REDACTED]

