8.1.8 Time to First Asthma Exacerbation (any severity)

Time to first exacerbation in days is defined as time from the first dose date to the first observed exacerbation date and will be calculated as:

Time to first exacerbation (days) = date of first exacerbation – date of first dose + 1

Subjects who do not experience any exacerbation will be censored at the last contact date of the subject.

Time to first exacerbation will be analyzed using Kaplan-Meier methodology ([Kaplan & Meier, 1958](#)). If estimable, the median time to first exacerbation, 25th and 75th percentiles with 2-sided 95% confidence intervals (CIs) will presented. Number and percentage of subjects with exacerbation events will also be presented.

8.1.9 Asthma symptoms, use of controller (standard) and rescue medications, nighttime awakening due to asthma and asthma-related activity limitations – Responses to a Questionnaire (as recorded on an eDiary)

Subjects will be recording their responses to 6 morning questions and 9 evening questions daily related to their Asthma. The questions are as follows (MQ=Morning Question, EQ=Evening Question) with a brief description of possible responses:

A horizontal bar chart consisting of 15 solid black bars of varying lengths. The bars are arranged in a staggered, non-overlapping pattern, creating a sense of depth or sequence. The lengths of the bars range from approximately 10% to 100% of the total width of the chart area. The bars are set against a plain white background.

This document is confidential

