8.1.10 Annualized Rate of Asthma Exacerbations (of any severity)

The number of asthma exacerbations will be calculated for each subject. A follow-up duration in years for each subject will be calculated as:

Follow-up duration (years) = (last contact date – date of first dose + 1) / 365.25, rounded to 2 decimal places.

The annualized rate of asthma exacerbations i.e. number of asthma exacerbation per subject year will be calculated as total number of asthma exacerbations for all subjects / total follow-up duration in years for all subjects.

Rate of asthma exacerbation will be tabulated, and a by-subject listing of all exacerbations will be created.

In addition, duration of asthma exacerbations in days is calculated as (the end date – the start date)+1. If asthma exacerbation is ongoing, the missing end date will be imputed as last known visit date. If a subject has multiple asthma exacerbations, each event will be counted separately.

The primary criterion for asthma exacerbations will also be summarized by criterion in number and frequency format. All asthma exacerbations will be included in this summary, a subject may have more than one exacerbation event.

[REDACTED]

[REDACTED]

[REDACTED]

[REDACTED]

[REDACTED]

[REDACTED]

This document is confidential.

[REDACTED]

10 Safety

All safety analyses will be performed using the Safety Population.

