10.8 Physical Examination

A complete physical examination will be done at Screening. A targeted physical exam will be done at all other scheduled visits except Day 4. All clinically significant abnormalities will be recorded either as medical history or adverse event based on the occurrence of the abnormality prior to or after the Baseline visit.

Physical examination findings prior to the first dose of study drug administration will be recorded on the medical history eCRF; clinically significant findings after the first study drug dose will be recorded as AEs.

At a minimum, the complete physical examination will include assessments of the skin, head and neck, lungs, cardiovascular (CV) system, abdomen, thyroid, and extremities. A targeted physical examination will include assessment of the lungs and any new subject complaints or changes from baseline.

A by-subject listing will be created for physical examination data.

[REDACTED]

[REDACTED]

This document is confidential.

[REDACTED]

12 Changes from Analysis Planned in Protocol

There are no changes from the analyses planned in the protocol.

This document is confidential.

This document is confidential.

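### SAP 7.4 adds a whole year to a calendar-year difference, so time since asthma diagnosis is reported 0 to 2 years too long

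*SAP*

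**What the plan says.** SAP 7.4 describes the variable as time from initial diagnosis to the first dose date, to be shown with continuous summary statistics for the Safety Population. The rule is: "Time from diagnosis of asthma in years will be calculated as (year of first dose – year of diagnosis) + 1". The section adds that the year of diagnosis will always be available, and gives no reason for the added 1.

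Protocol 10.2.2 has the site collect "Date of diagnosis of asthma" in the Screening medical history. Protocol 13.5 lists the variable as "time from diagnosis of asthma to Screening", without a formula. SAP section 12 states: "There are no changes from the analyses planned in the protocol".

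For comparison, SAP 8.1.8 uses "Time to first exacerbation (days) = date of first exacerbation – date of first dose + 1", where the unit is days. SAP 8.1.10 defines each subject's follow-up in years as a day count divided by "365.25, rounded to 2 decimal places", and the annualized rate as "total number of asthma exacerbations for all subjects / total follow-up duration in years for all subjects".

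**The concern.** In a day count, adding 1 makes the first and last day both count, and costs at most one day. In SAP 7.4 nothing is counted in days, so the added 1 is a whole year. The result is the number of calendar years touched by the interval, which is not the elapsed time that the section says it measures.

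At stake is a reported description of who was studied. Disease duration would be overstated in the summary table and the listing, and the bias would not shrink with more subjects.

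**Working it through.** The plan gives a formula and no numerical result, so there is no stated figure to reproduce. The check is of the formula itself.

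**Inputs.** The rule and the target quantity come from SAP 7.4. The spread of dates within the year is not in the documents and is assumed where stated.

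**Algebra.** Let u and v be the fractions of the calendar year elapsed at first dose and at diagnosis, each from 0 to just under 1, and let D be the difference in calendar years.

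- True elapsed time = D + (u − v)
- SAP 7.4 = D + 1, so its error is 1 − (u − v), strictly between 0 and 2 years
- Plain difference = D, so its error is −(u − v), strictly between −1 and +1 year

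So the added 1 contributes exactly 1 year to everyone. The further spread of up to 1 year either way comes from using years only, and is there with or without it.

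**Examples** (elapsed = days / 365.25):

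| Diagnosis | First dose | Elapsed | SAP 7.4 (error) | Plain difference (error) |
|---|---|---|---|---|
| 1 Jan 2010 | 31 Dec 2019 | 9.996 | 10 (+0.004) | 9 (−0.996) |
| 1 Jul 2010 | 1 Jul 2019 | 8.999 | 10 (+1.001) | 9 (+0.001) |
| 31 Dec 2015 | 1 Jan 2019 | 3.003 | 5 (+1.997) | 4 (+0.997) |
| 31 Dec 2019 | 1 Apr 2020 | 0.252 | 2 (+1.748) | 1 (+0.748) |
| 2 Jan 2019 | 2 Dec 2019 | 0.914 | 1 (+0.086) | 0 (−0.914) |

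**Average error, assuming u and v independent and uniform.** The variance of u − v is 1/12 + 1/12 = 1/6.

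- With the added 1: mean 1.0 year, root mean square error √(1 + 1/6) = 1.08 years
- Without it: mean 0, root mean square error √(1/6) = 0.41 year
- The plain difference is closer to the truth whenever u − v < 1/2, which has probability 1 − (1/2)²/2 = 7/8 = 87.5%

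**Sensitivity to season, with only v uniform.** The mean excess with the added 1 is 1.5 − u, from 1.5 years for first dose on 1 January to 0.5 on 31 December. Root mean square errors with and without the added 1 are 1.53 and 0.58 (1 January), 1.04 and 0.29 (mid-year), and 0.58 and 0.58 (31 December). The added 1 is never better on this measure and ties only at year end.

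**Relative size.** A 1-year excess is 1/5 = 20% of a true 5 years and 1/20 = 5% of a true 20 years (assumed durations).

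**End point: Screening or first dose.** The protocol synopsis says "The Screening Period duration will be up to 4 weeks", with at least 2 weeks of baseline assessments. In calendar years, the choice matters only if those weeks cross 1 January. With first doses uniform over the year (assumption), that is 14/365.25 = 3.8% to 28/365.25 = 7.7% of subjects, or 0.04 to 0.08 year in the mean.

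**Rounding in SAP 8.1.10, read literally.** If last contact falls within 2 days of Day 85 (assumption), the rate error is (d/365.25) / (its 2-decimal value) − 1:

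- 83 days: 0.2272/0.23, −1.2%
- 84 days: 0.2300/0.23, 0.0%
- 85 days: 0.2327/0.23, +1.2%
- 86 days: 0.2355/0.24, −1.9%
- 87 days: 0.2382/0.24, −0.8%

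With 4 events in 40 subjects at 85 days (assumption), the rate is 4/(40 × 0.2327) = 0.430 unrounded and 4/(40 × 0.23) = 0.435 rounded. The exact Poisson 95% interval is 0.12 to 1.10, so the effect is negligible.

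**The case against.** The best case against raising this is that almost nothing depends on it. The variable is descriptive, the study has at most 40 subjects and SAP 6.1 rules out formal hypothesis testing. No endpoint, eligibility criterion or covariate in the visible text uses the variable. The rule is printed openly and the added 1 is constant, so a reader can subtract it. All of that stands, and it limits the weight of the point. It does not make the reported figure right.

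A second defence is that the year-only rule copes with partial diagnosis dates. That may explain the use of years, but not the added 1: with unknown months and evenly spread dates, the plain difference already has mean error zero.

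Third, deleting the 1 is not a perfect cure. An error of up to 1 year either way remains, and a same-year diagnosis reads 0. Using full dates where they were recorded would be better still. That is a fair refinement and no reason to keep the present formula.

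Fourth, the end-point difference may be no more than detail that Protocol section 13 leaves to the SAP. The rounding may be for display only: SAP 7.1 uses similar wording for weeks of follow-up, which are simply summarised. The public copy also lacks some SAP text, including the section 6.3 that SAP 10.3 cites, so only the visible text is silent on rounding. Neither point would merit a comment alone.

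**Conclusion.** The formula in SAP 7.4 is wrong as written, and this follows from the algebra without assumptions: reported time since diagnosis exceeds the elapsed time by more than 0 and less than 2 years for every subject. The mean excess of 1.0 year, the root mean square errors and the 87.5% figure rest on dates spread evenly within the year. If only diagnosis dates are even, the mean excess lies between 0.5 and 1.5 years, depending on the date of first dose.

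This is an optional correction. Differences between groups are unchanged, and no safety or efficacy result is touched. The end-point mismatch is real in wording but nearly immaterial. The rounding point holds only on a literal reading and is negligible.

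**What to change.** - **SAP 7.4:** delete the added 1. Where month and day of diagnosis were recorded, the SAP could instead use (first dose date − diagnosis date) / 365.25, with the plain year difference for partial dates; this is a refinement, not a necessity.
- **End point:** use Screening or first dose in both documents, or list the difference in SAP section 12.
- **SAP 8.1.10:** state that rounding is for display only. Sum unrounded days over subjects, divide by 365.25 once, then round.

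The cost is one deletion, one clause and one line in SAP section 12, with no new data. Aligning the end point through Protocol 13.5 instead would need a protocol edit. The one drawback of the plain year difference is that subjects diagnosed in the calendar year of first dose show 0 years, which a table footnote can explain.
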